3.1 General Description

Patients will receive the following multi-modal pain regimen in addition to the adductor canal pain catheter.

Preoperative (All patients receive the following in the pre-op holding):

Acetaminophen 1000 mg oral

Celebrex 400 mg oral

Dexamethasone 10 mg IV

Intraoperative (All patients receive the following):

Periarticular block

- Ketorolac 30 mg with weight-based ropivacaine and epinephrine, diluted in normal saline to a total volume of 120 mL (50-74.9 kg – ropivacaine 200 mg, epinephrine 0.1 mg), (75 – 99.9 kg – ropivacaine 300 mg, epinephrine 0.2 mg), (100 kg and greater – ropivacaine 400 mg , epinephrine 0.3 mg).

Postoperative:**Adductor canal pain catheter (saline or ropivacaine)**

Acetaminophen 1000 mg oral every 6 hours scheduled

Tramadol 50 mg oral every 6 hours as needed

Dexamethasone 10 mg IV scheduled daily while hospitalized (*max 3 days*)

Toradol 10 mg oral every 6 hours scheduled daily while hospitalized (*max 3 days*)

Oxycodone 5 mg every 3 hours as needed for pain

Dilaudid 0.5 mg IV push every 3 hours as needed for pain > 8 on VAS score

Discharge:

Acetaminophen 1000 mg oral every 6 hours scheduled (x2 weeks)

Tramadol 50 mg oral every 6 hours as needed for pain

Celebrex 400 mg oral scheduled daily (x2 weeks)

Oxycodone 5 mg every 3 hours as needed for pain

[figure not shown]
At the time of discharge, medications will be filled for two weeks. Patients will report their pain scores during this time via electronic and phone surveys. If additional pain medications are required these will be filled per the treating physician's discretion.

3.2 Number of Subjects

Twenty eight patients will be recruited into each arm, for a total of 84 patients. This will serve as a pilot study to determine feasibility.

3.3 Duration of Participation

Results will be collected daily for 14 days postoperatively, followed by weekly questionnaires until patients discontinue narcotic medication. Additional questionnaires will be collected at 30 and 60 days postoperatively in order to record pain and KOOS Jr. scores.

3.4 Primary Study Endpoints

The primary endpoint will be pain scores, calculated by the Numerical Rating Scale. This score will be collected daily during the hospital examination and by online or phone surveys after discharge. We will calculate the mean difference in recorded pain scores between cohorts. We hypothesize that the intermittent bolus infusion cohort will report improved pain scores compared to continuous infusion catheters.

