1.5 Risks and Benefits

The benefits of the study will be to evaluate the efficacy of the differing modes of medication delivery through the adductor canal pain catheter. If optimized, we believe this will allow us to continue to reduce the amount of narcotic medications prescribed following orthopedic surgery.

All components of the multimodal pain regimen are currently safely used in orthopedic patients. There is a theoretical risk of renal damage or GI upset with the use of anti-inflammatory medications, but we have not seen this with our total knee study. There is also the possibility that patients will have uncontrolled pain following surgery. These patients will have IV narcotic medication as a safety net during their hospitalization and will be able to utilize our standard opioid regimen upon discharge.

2 Study Objectives

Primary Objective

The primary objective will be to compare postoperative pain levels between the treatment groups, using the Numerical Rating Scale (NRS).

Secondary Objective

The secondary objectives will be to compare the amount of patient-administered medication use between groups as well as duration of narcotic use between groups.

3 Study Design

This project will be conducted as a three-arm double-blinded, randomized controlled trial comparing differing modes of medication dispersion using the adductor canal pain catheters. The three arms will be a single shot adductor canal block (with saline filled catheter) compared to ropivacaine 0.2% continuous infusion, and ropivacaine 0.2% intermittent bolus infusions. Treatment groups will be assigned to patients using computer-based randomization via the dynamic allocation method of Pocock and Simon. Subjects will be screened in the outpatient clinic setting and those interested and eligible will be consented and enrolled in the trial.

A total of 84 patients will be enrolled in this study. Twenty eight patients will be in each comparison group. After enrollment patients will undergo randomization by the research pharmacy in order to maintain blinding of the surgical team, nursing staff, and patient. The patient will then undergo their surgical procedure and receive a multi-modal pain regimen as described below. All treatment groups will receive the same regimen with the exception of the adductor canal catheter. All of the patients will have the catheter placed in the Post Anesthesia Care Unit following

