surgery and bolused with 10 mL of 0.5% ropivacaine. The pumps will be loaded with saline (single shot adductor canal group), or ropivacaine 0.2%, dispersed in either a continuous infusion (6 mL/hr) or pulsed intermittent bolus (8 mL every 2 hours). All groups will have a patient demand dose of 6 mL/hr for anterior knee pain. The medication for the adductor catheter will be dispersed to the anesthesia team by the research pharmacy. The anesthesia team will place the catheter under ultrasound guidance in the recovery room. They will adjust the delivery mode based on patient randomization. The anesthesia team will record the serial number of the pump at the time of placement.

Questionnaires will be sent electronically to the patient. Results will be collected daily for 14 days postoperatively, followed by weekly questionnaires until they discontinue narcotic medications. Additional questionnaires will be collected at 30 and 60 days postoperatively in order to record pain and KOOS Jr. scores. The questionnaires will be sent in the morning; if a patient fails to fill out the questionnaire by the afternoon, a member of the research team will contact the patient to obtain the data. The questionnaires will document numerical rating scale (NRS) pain scores, information on symptoms of nausea, vomiting, and constipation, and will inquire if the patient is still consuming narcotic medication.

Following discontinuation of the catheter the patient will remove and return the device to the supplier. The supplier will then provide the rate of on-demand usage to the research team by way of device serial number. This information will be stored in Redcap.

Subjects will be withdrawn prior to completion if they ask to be removed from the study. They may also be withdrawn from the study if they have a serious adverse reaction to one of the prescribed medications. Finally, subjects may be withdrawn at the discretion of the treating physician. If subjects are withdrawn early their last recorded pain score will be carried forward until study conclusion in order to perform intention to treat analysis. The study will continue to ascertain duration of narcotic use with weekly questionnaires, until the patient has stopped the medication.

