3.7 Identification of Source Data

The following source data will be directly recorded on the Case Report Form (CRF) at the pre-op visit and inputted into REDcap, a password protected database.

- Name
- Medical Record Number
- Email address
- Date of Birth, Age
- Gender
- Race
- Weight (lbs), Height (In), BMI
- Previous surgeries? (yes, no)
- Are you taking Nsaids? (yes, no)
- Previous injections (yes, no)
- Baseline NRS score
- Laterality of surgery
- KOOS Jr. Questionnaire
- Device serial number

The following source data will be recorded daily for two weeks using an online questionnaire recorded into REDcap, and continued weekly until discontinuation of narcotic medication. This data will again be collected at 30 and 60 days following the date of surgery.

- Name
- Medical Record Number
- Date of Birth
- How long has it been since your operation? (Less than 1 month, 1-2 months, Greater than 2 months)
- Are you using narcotic medication? (yes/no)
 - What was the date you last consumed narcotic medication? (if no to previous answer)
- How would you rate the pain you have been experiencing? (0-10)

- Have you been experiencing constipation over the past 24 hours? (yes, no)
- Have you been vomiting or had dry-retching over the past 24 hours? (once, twice, three or more times, no)
- Have you been experiencing a feeling of nausea (an unsettled feeling in the stomach and slight urge to vomit) over the past 24 hours? (yes, no)
- KOOS Jr. Questionnaire (only recorded during 1 month and 2 month questionnaires)
- Rate of on-demand catheter use (recorded at final survey only)

4 Subject Selection Enrollment and Withdrawal

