5.9.4 Return or Destruction of Study Drug

After the medication has been fully dispensed (postoperative day #4), patients will remove the adductor catheter and send the pump to Avanos for processing.

6 Study Procedures

6.1 Visit 1

At visit #1 patients will be screened for eligibility for inclusion in the study. If agreeable, an informed consent will be signed.

6.2 Visit 2

[figure not shown]
Patients will undergo standard preoperative clearance testing.

6.3 Visit 3

Patients will then proceed with the total knee replacement procedure. During the hospitalization we will record daily pain, nausea, vomiting, and constipation levels. Following the hospitalization these values will continue to be recorded daily utilizing an online questionnaire. If patients fail to complete the questionnaire then we will contact the patient via phone to record the daily value.

6.4 Visit 4

At 2 weeks the patients will return for a standard postoperative visit. The patient will then receive an online questionnaire weekly until they discontinue narcotic medication. They will receive additional surveys at 30 and 60 days following surgery.

7 Statistical Plan

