7.2 Statistical Methods

Descriptive and Inferential Statistics

Continuous variables will be summarized with the sample mean, median, standard deviation, minimum, 25th percentile, 75th percentile, and maximum. Categorical variables will be summarized with number and percentage of patients. All analysis will be performed on the basis of the intention-to-treat principle. Comparisons of endpoints between the three treatment arms will be made using a Wilcoxon rank sum test (continuous or ordinal endpoints) or Fisher's exact test (categorical endpoints). Missing data will be imputed using either the last observation carried forward method, a regression-based approach, or another method, depending on the extent of missing data. In order to adjust for the three pair-wise comparisons between treatment groups that will be made for each endpoint, we will utilize a Bonferroni correction for multiple testing, after which p-values of < 0.0167 will be considered as statistically significant. All statistical tests will be two-sided.

Primary Hypothesis:

We hypothesize that the intermittent bolus infusion cohort will report improved pain scores compared to continuous infusion catheters and placebo cohorts.

Secondary Hypothesis:

We hypothesize that the intermittent bolus cohort will require fewer doses of patient-administered medication and will use narcotic medication for a shorter duration when compared to the continuous infusion and placebo groups.

Interim Analysis

We will evaluate the first twenty patients. If 50% of the patients are withdrawn from the study for poor pain control or serious adverse reactions to the study medication, then we will close the study early.

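### The primary NRS pain endpoint has no fixed day or window and no one-value-per-patient rule, and the 0.0167 threshold does not cover a choice among the possible readings

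*Combined protocol and SAP*

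**What the plan says.** - **Endpoint.** Section 3.4 names NRS pain scores as primary and says: "We will calculate the mean difference in recorded pain scores between cohorts". The objective in Section 2 and the primary hypothesis in Section 7.2 give no time point either.
- **Test.** Section 7.2 assigns a rank test ("Comparisons of endpoints between the three treatment arms will be made using a Wilcoxon rank sum test (continuous or ordinal endpoints"). It mentions no repeated-measures model. Its Bonferroni correction is for the three pairs of arms within each endpoint, two-sided, with significance declared below 0.0167.
- **Scores available.** Section 3.7 has the questionnaire "recorded daily for two weeks using an online questionnaire recorded into REDcap, and continued weekly until discontinuation of narcotic medication". Sections 3.3 and 3.7 add days 30 and 60.
- **Treatment period.** Section 5.9.4: "After the medication has been fully dispensed (postoperative day #4), patients will remove the adductor catheter". The Study Summary also gives four days of administration.
- **Withdrawn patients.** Section 3 (Study Design) says "their last recorded pain score will be carried forward until study conclusion in order to perform intention to treat analysis". Section 7.2 leaves the imputation method open, and Section 7.3 describes the analysed patients as those who completed the study.
- **Purpose.** Sections 3.2 and 7.1 describe a pilot sized for feasibility, whose data will be used to power a larger trial.

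**The concern.** A rank sum test compares one number per patient. Each patient is due to give 16 scores, plus weekly ones while narcotics continue, and the plan does not say how these become one number. At least four analyses fit the text: a mean over days 1–4, a mean over days 1–14, a mean of all recorded scores, and a separate test on each day. They answer different questions and can disagree. If the choice is made once results by arm are visible, the stated threshold no longer describes the error rate.

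The reading closest to the words, all recorded scores, has a further weakness. Weekly scores exist only for patients still taking narcotics, and duration of narcotic use is itself a secondary endpoint (Section 3.5). A post-randomisation outcome would then decide which scores enter the primary comparison.

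**Working it through.** **The plan's own figures.** 0.05/3 = 0.0167, and 3 × 28 = 84. Both agree with the text. No power figure is stated.

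**Scores per patient.** Days 1–14, 30 and 60 give 16 fixed scores. Weekly scores on days 21, 28, 35, 42, 49 and 56 add up to 6 by day 60, so at most 22 by then. With the catheter in to day 4, the scores after it number 10 of 14, 12 of 16 or 18 of 22.

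**Dilution.** Let k scores fall in the catheter period, n be the number averaged with equal weight, and f the share of the effect that persists afterwards. The share kept is (k + (n − k)f)/n. With k = 4:

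| Average | f = 0 | f = 0.5 | f = 1 |
|---|---|---|---|
| Days 1–4 | 4/4 = 100% | 100% | 100% |
| Days 1–14 | 4/14 = 29% | 9/14 = 64% | 100% |
| 16 fixed scores | 4/16 = 25% | 10/16 = 63% | 100% |
| 22 scores (patient with all six weekly scores) | 4/22 = 18% | 13/22 = 59% | 100% |

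If the day-4 score reflects the time after removal (k = 3, f = 0), the 14-day and 16-score means keep 3/14 = 21% and 3/16 = 19%, and the days 1–4 mean keeps 3/4 = 75%.

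**Whole-arm figure with weekly scores included.** Assume 20% of patients give 22 scores and 80% give 16: 0.8 × 4/16 + 0.2 × 4/22 = 23.6%. The 20% is an assumption. It matches the share of the oxycodone group in the earlier trial (Section 1.1) still needing narcotics at 60 days.

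**Error rate.** Simulation with no true difference, 28 per arm, normal scores and several assumed within-patient correlation patterns, for one pair of arms at a nominal 0.0167:
- taking the best of days 1–4, days 1–14 or the 16 fixed scores rejects in about 0.02 to 0.03 of trials;
- rejecting if any of 14 daily tests passes does so in about 0.09 to 0.14.

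These depend on the assumed correlations. The limits that hold whatever the correlation are 3 × 0.0167 = 0.05 and 14 × 0.0167 = 0.23. Day-by-day testing of all pairs would be 14 × 3 = 42 tests, against a correction for three.

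**Narcotic-conditional scores.** Assume 20% of one arm and none of the other stay on narcotics to day 60, and pain falls linearly through 5, 2.5 and 1.5 on days 1, 14 and 60.
- Sum of days 1–14: 14 × 3.75 = 52.5. Day 30: 2.5 − 16/46 = 2.15. Day 60: 1.5. The 16-score mean is 56.15/16 = 3.51.
- Sum of the six weekly scores: 15 − 147/46 = 11.80. The 22-score mean is 67.96/22 = 3.09.
- Shift in that arm's mean: 0.20 × (3.09 − 3.51) = −0.08.

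Other assumed curves give 0 to −0.13 for per-patient means. If scores are pooled instead, the shift runs from −0.17 to +0.06; the positive value arises when the continuing users are a subgroup with more pain.

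**Carry-forward.** If the Section 3 rule governs and a patient's last score is on day 2, carried values make up 2/4 = 50% of a days 1–4 mean, 12/14 = 86% of a 14-day mean and 14/16 = 88% of the 16 scores. The Study Summary lets participation run past day 60 while narcotics continue, so study conclusion is not a fixed day.

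**The case against.** The best defence is that this is a feasibility pilot with no power claim, so an imprecise endpoint does limited harm. That softens the point. It does not answer it, because Section 7.2 still declares significance, and Section 7.1 relies on these data to plan a larger trial, which needs a defined endpoint and its variability.

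A second defence is that complete loss of effect at catheter removal is an extreme case. Section 1.3 links early pain control to later refills and hypothesises a link to long-term opioid use, so some carry-over is plausible. This stands: the dilution ranges from severe to none, and the no-persistence figures are one end. Under day-by-day testing there is no dilution at all, and the issue becomes multiplicity.

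Some stronger readings are tempting but not supported:
- A reader might take 18% as the loss for a whole arm. It needs every patient to give all six weekly scores, that is, to be on narcotics to about day 56.
- A reader might infer that the narcotic-conditional scores favour a particular arm. Their effect is small in the cases worked, and its sign changes with the assumptions.
- A reader might infer that each hospital day yields two competing scores, because Section 3 describes daily questionnaires in general terms. Sections 3.4, 5.5 and 6.3 place the surveys after discharge, so the two sources are largely sequential.
- Nothing in the documents suggests an intention to pick a favourable window. The point is that the text would not prevent it.

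**Conclusion.** The concern holds: no section fixes the window or the per-patient value for the primary comparison, and the multiplicity correction does not reach that choice. The dilution figures assume four catheter-day scores and equal weights; how much is lost turns on persistence, which the documents do not give. The error-rate inflation is modest for a choice among three windows and larger for daily testing, under assumed correlations. The narcotic-conditional scores are a lesser problem of principle, with no direction claimed. This should be fixed before arm-level data are seen. The need for one fixed window does not depend on any of these assumptions; which window to choose is the team's judgement.

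**What to change.** State in Sections 3.4 and 7.2, before any arm-level data are seen, wording such as: *The primary endpoint is each patient's mean of one NRS score per calendar day over postoperative days 1 to X, the same for all patients. Each pair of arms is compared once by Wilcoxon rank sum test at 0.0167.*

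- The team sets X. X = 4 matches the infusion period. X = 14 uses all the daily scores and fits the general wording of the objective, but the possible dilution should then be acknowledged.
- Leave the narcotic-conditional weekly scores out of the primary average.
- Report individual days, and days 30 and 60, as secondary.
- End any carry-forward for the primary endpoint on the last day of the window. Changing Section 3 alone is not enough: its rule must be reconciled with the open choice of imputation method in Section 7.2 and the completers wording in Section 7.3.

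The cost is wording. Daily scores to day 14 and scores at days 30 and 60 are already scheduled, and classing by calendar day needs no removal time. The downside is that one window must be chosen and defended, and pain outside it becomes secondary.

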3.5 Secondary Study Endpoints

The secondary endpoints will be the amount of medication administered via the patient-controlled function on the adductor catheter as well as duration of narcotic use required in each cohort. We hypothesize that the intermittent bolus cohort will require fewer doses of patient-administered medication and will use narcotic medication for a shorter duration when compared to the continuous infusion and placebo groups.

We will additionally calculate the overall morphine equivalents used in each cohort during their hospitalization, and dividing this by the total number of post-surgical hospitalization hours in order to normalize the data.

Nausea and vomiting will be recorded daily using the postoperative nausea and vomiting scale and compared between groups. Presence of constipation will be a subjective rating by the patient that is also recorded daily. We will compare the post-surgery length of hospitalization between groups. Finally, we will compare patient-reported outcomes using the KOOS Jr. questionnaire.

We hypothesize that the intermittent bolus cohort will use less narcotic mediation and will therefore have lower rates of constipation, nausea and vomiting. Furthermore, we believe this cohort will demonstrate equivalent lengths of stay and patient-reported outcomes as compared to the comparison groups.

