9.3 Case Report Forms

The study case report form (CRF) is the primary data collection instrument for the study. All data requested on the CRF must be recorded. All missing data must be explained. If a space on the CRF is left blank because the procedure was not done or the question was not asked, write "N/D". If the item is not applicable to the individual case, write "N/A". All entries should be printed legibly in black ink. If any entry error has been made, to correct such an error, draw a single straight line through the incorrect entry and enter the correct data above it. All such changes must be initialed and dated. Do not erase or use "white-out" for errors. For clarification of illegible or uncertain entries, print the clarification above the item, then initial and date it. If

the reason for the correction is not clear or needs additional explanation, neatly include the details to justify the correction.

Data Management

Data will be verified by the investigator after each subject visit, then entered into REDcap database.

Data Processing

REDCap data will be exported into statistical software and analyzed.

Data Security and Confidentiality

All data will be stored on password and access protected shared drives. These drives contain archives with audit trails indicating the date, time, and person ID when the data is accessed. The patient information will be de-identified through the use of study IDs.

Data Quality Assurance

Data quality is checked during the archiving and organization process. Paper data is reviewed prior to scanning and e-filing.

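### The plan specifies no use of the pre-operative KOOS Jr. score when KOOS Jr. is compared between arms at 30 and 60 days, which gives up precision the trial could have at no data cost

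*Combined protocol and SAP*

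**What the plan says.** Section 3.7 opens its first list with "The following source data will be directly recorded on the Case Report Form (CRF) at the pre-op visit", and KOOS Jr. is on that list. Section 9.3 adds "All data requested on the CRF must be recorded" and requires any missing item to be explained, so a baseline score is planned for every patient.

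The post-operative measurements are set in 3.3: "Additional questionnaires will be collected at 30 and 60 days postoperatively in order to record pain and KOOS Jr. scores". The second list in 3.7 agrees: "KOOS Jr. Questionnaire (only recorded during 1 month and 2 month questionnaires").

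Section 3.5 states the endpoint in one sentence, "Finally, we will compare patient-reported outcomes using the KOOS Jr. questionnaire", without naming a time point, a change score, a covariate or a model. It also gives an expectation: "we believe this cohort will demonstrate equivalent lengths of stay and patient-reported outcomes as compared to the comparison groups".

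Section 7.2 supplies the test: "Comparisons of endpoints between the three treatment arms will be made using a Wilcoxon rank sum test (continuous or ordinal endpoints"). The three pairwise comparisons are Bonferroni-corrected, "after which p-values of < 0.0167 will be considered as statistically significant". No section mentions the pre-operative KOOS Jr. score in connection with any comparison.

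**The concern.** The same patient answers the same questionnaire before surgery and twice after it. If the scores are correlated, part of the spread at 30 and 60 days is already present before treatment and can be removed. A rank sum test on follow-up scores leaves it in the error term.

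Two things follow with 28 patients per arm. The estimated difference is less precise than it could be, which matters because 3.5 expects the arms to be alike on this endpoint: a statement of that kind needs a narrow interval, not a non-significant p-value. And if two arms happen to differ before surgery, part of that difference appears as a difference after surgery. Section 3 names Pocock and Simon dynamic allocation but lists no balancing factors, so balance on KOOS Jr. cannot be assumed.

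**Working it through.** **Inputs from the plan.** 28 per arm, 84 in all (7.1); two-sided tests; a 0.0167 threshold (7.2). The threshold reproduces: 0.05 / 3 = 0.0167. The sample size rests on feasibility (7.1), so there is no power figure to reproduce.

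**Assumptions.** The plan gives no SD, effect size or correlation. I work in SD units with normal data, a true difference of 0.8 SD, and rho from 0.1 to 0.5.

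**1. Precision.** Adjustment multiplies the residual variance by (1 − rho²). Estimating the slope costs a factor of about 1 + 1/(2n − 4) = 1 + 1/52 = 1.019 for two arms of n = 28. The interval width relative to the unadjusted one is the square root of (1 − rho²) × 1.019:

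- rho 0.1: √(0.99 × 1.019) = 1.004, very slightly wider
- rho 0.2: √(0.96 × 1.019) = 0.989, 1% narrower
- rho 0.3: √(0.91 × 1.019) = 0.963, 4% narrower
- rho 0.5: √(0.75 × 1.019) = 0.874, 13% narrower

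Simulated interval widths agree.

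**2. Power for 0.8 SD, 28 against 28, two-sided 0.0167.** The unadjusted t-test has non-centrality 0.8 × √(28/2) = 2.99 on 54 degrees of freedom, which gives 70%. The other figures are simulated (40,000 trials; 8,000 for the Wilcoxon test):

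| rho | Wilcoxon | t-test | ANCOVA | ANCOVA minus t-test |
|---|---|---|---|---|
| 0.1 | 67% | 70% | 69% | about −1 point |
| 0.2 | 67% | 70% | 71% | about 1 point |
| 0.3 | 67% | 70% | 74% | 3 to 4 points |
| 0.5 | 67% | 70% | 83% | about 13 points |

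The last column isolates the effect of the covariate. The further 3 points or so between Wilcoxon and t-test come from the normality assumption and should not be credited to adjustment.

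**3. Chance imbalance.** If allocation does not balance on KOOS Jr., the baseline difference between two arms has SD √(2/28) = 0.27. Its 95% range is ±1.96 × 0.267 = ±0.52 SD. An unadjusted comparison carries over rho times the imbalance:

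- rho 0.5: 0.5 × 0.52 = 0.26 SD
- rho 0.3: 0.3 × 0.52 = 0.16 SD

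These are shifts at the edge of the 95% range, not maxima. A given pair of arms differs by more than 0.25 SD with probability 35%, and at least one of the three pairs does with probability 62%.

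**4. Type I error.** With no true difference the Wilcoxon test rejected in 1.5% to 1.7% of simulated trials (4,000 per value of rho), against a nominal 1.67%. In the roughly 1,000 of those trials with a baseline imbalance of at least 0.3 SD, it rejected in about 2.2% at rho 0.3 and 3.5% at rho 0.5. The problem is conditional on an imbalance; the overall rate holds.

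**The case against.** The strongest objection is that the plan never says the follow-up score is analysed raw. Section 7.2 names a test, not the variable it is applied to, and a rank sum test on change from baseline would fit the text. That much stands: the absence of adjustment follows from a general rule, not from a statement about KOOS Jr. But a change score is not written anywhere either, and it would be a poorer use of the baseline at low correlation. Its variance is 2(1 − rho), or 1.4 at rho 0.3, and simulated Wilcoxon power for 0.8 SD is then 49% against 66% for the follow-up score alone. The two are about level at rho 0.5.

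Second, this is a pilot sized for feasibility (3.2, 7.1), KOOS Jr. comes last among the secondary endpoints, and 3.5 does not expect a difference on it. Power for 0.8 SD is therefore an imperfect yardstick. This stands and limits the importance of the point, but the narrower interval is useful whether or not a difference is expected.

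Third, the benefit depends on a correlation that the plan does not give, with a joint replacement between the two measurements. This also stands: a material gain needs rho near 0.5.

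A reader might infer that the planned test is invalid or inflates false positives. The documents do not support that: allocation is randomised and the overall error rate stays near nominal. Nor do they show that adjustment was considered and rejected; they are silent.

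**Conclusion.** The point holds as a low-cost improvement, not as an error that undermines the trial. A baseline KOOS Jr. score is collected, and no use of it in the comparison is specified.

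The size depends on the assumed correlation. At rho 0.5 the gain is material, in both power and interval width; at 0.3 it is small, at 0.2 marginal, and below that negligible. These figures assume normal data, complete scores and 28 per arm.

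One further inference should be resisted. Adjustment would not by itself let the trial conclude that the arms are alike on patient-reported outcomes. Section 3.5 gives no margin for that expectation, and this change does not supply one.

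**What to change.** In 7.2, state that KOOS Jr. at 30 days and KOOS Jr. at 60 days will each be compared by ANCOVA on treatment arm, with the pre-operative KOOS Jr. score as covariate. Report the three adjusted pairwise differences at each time point with confidence intervals at the Bonferroni level (98.33%, that is 1 − 0.05/3). Keep the unadjusted Wilcoxon test as a pre-specified sensitivity analysis. Fix the main method in advance, with no switch that depends on how the residuals look.

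The cost is one or two sentences in 7.2, one model per time point and one degree of freedom for the covariate. No new data are needed. If the correlation turns out to be very low, the loss is slight: about half a percent in interval width at rho 0.1.
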